# 9.2.5 Treatment-Emergent Adverse Events

A treatment emergent adverse event (TEAE) is defined as any event not present prior to the initiation of study treatment or any event already present that worsens in either intensity or frequency following exposure to the treatment.

# 9.2.6 Unexpected Adverse Event/Adverse Drug Reaction

An unexpected AE/ADR is an AE/ADR for which the nature or severity is not consistent with the applicable product information (e.g., not clearly listed in the Reference Safety Information of the IB for an unapproved investigational product, or in the summary of product characteristics [SmPC] for an authorised product).

The term "expected" in pharmacovigilance is not used to describe an event which might be anticipated from knowledge of the pharmacological properties of a substance. An event is also not to be described as "expected", merely because it was foreseeable due to the health status (e.g., age, medical history) of the study patient. It refers strictly to the event being mentioned or listed in the applicable product information.

#### 9.3 SERIOUS ADVERSE EVENTS

A Serious Adverse Event (SAE) is any untoward medical occurrence that at any dose:

- Results in death (other than due to disease progression, see Note below).
- Is life-threatening\*.
- Requires in-patient hospitalisation or prolongation of existing hospitalisation.
- Results in persistent or significant disability/incapacity.
- Is a congenital anomaly/birth defect.
- Other medically important condition. For example conditions not included above but that may jeopardize the patient or may require intervention to prevent one of the outcomes listed above unless clearly related to the patient's underlying disease. Examples of important medical events which may also meet the definition of a SAE include: intensive treatment in an emergency room or at home for a reversible condition that did not result in hospitalisation (eg, allergic bronchospasm or convulsions).

All of the above criteria apply to the case as a whole and should not be confused with the outcomes of individual reactions/events. More than one of the above criteria can be applicable to the one event.

All SAEs, whether or not deemed related to IMM-101, nivolumab or ipilimumab, including those considered expected or associated with protocol-specified procedures must be reported to the relevant pharmacovigilance contact within 24 hours of knowledge by email or fax in the format detailed by the SAE Reporting Form (see Section 9.7).

**Note:** Death of a cancer patient due to disease progression may be expected in a study of cancer patients. Therefore, SAEs/death due to disease progression will not be captured as an SAE if the SAE/death is, in the Investigator's opinion, expected as normal course of the disease. However, if the disease progression was faster than expected then an SAE will be reported.

# 9.3.1 Suspected Unexpected Serious Adverse Reaction

A suspected, unexpected serious adverse reaction (SUSAR) is defined as a suspected adverse reaction related to the study drug which occurs during the study, and that is both unexpected (i.e., not previously identified in nature, severity, or degree of incidence based upon the current IB, Section 8) and serious.

\* Life-threatening in the definition of a SAE or adverse reaction refers to an event in which the patient was at risk of death at the time of event; it does not refer to an event, which hypothetically might have caused death if it were more severe.

Page 69 of 98

For all SAEs the Investigator and Sponsor (or designee) will independently assess whether there is a reasonable possibility that the event may have been caused by IMM-101 ("drug-related"). If the SAE is assessed to be drug-related by the Investigator or the Sponsor and is also unexpected, the Sponsor (or designee) will report it to the appropriate Regulatory Authorities and Ethics Committees and notify Investigators as required by applicable local regulations.

SUSARs are required to be reported within 7 calendar days for life threatening events and those resulting in death, or 15 calendar days for all others. These timeframes begin with the first notification of the SUSAR to the Sponsor/designee.

As nivolumab and ipilimumab are non-investigational products, any SAEs that are considered by the Investigator to be related to these products will be reported if it is considered a possibility that the SAE is a result of an interaction between IMM-101 and nivolumab or between IMM-101 and ipilimumab or if the adverse reaction is considered by the Sponsor as likely to affect the safety of patients in the study. Other adverse reactions considered related to nivolumab or ipilimumab, but not to IMM-101, will be reported by the Sponsor (or designee) to the applicable regulatory authority as post-approval SAEs.

#### 9.4 LABORATORY EVALUATION

Clinical laboratory evaluations will be assessed (prior to administration of IMM-101) using the parameters and timelines presented in **Table 1**.

Abnormal laboratory test results considered to be clinically significant will be recorded as an AE in the patient's eCRF and the patient will be followed-up until the laboratory value has returned to normal range or stabilised at a non-clinically significant value.

Any additional blood tests to those scheduled in this study will be performed as per the Investigator's routine procedures.

## 9.5 ASSESSING AND RECORDING SAFETY PARAMETERS

All AEs will be recorded on the patient's eCRF from the time of informed consent. All AEs will be followed until resolution, death, or 30 days after the last administration of study treatment (whichever comes first). The Investigator may contact the patient by telephone to obtain the information. Related SAEs will be recorded regardless of time from last dose and added to the eCRF if the occurrence is prior to final Investigator sign-off of the eCRF. SAEs will be recorded up to 30 days from the last administration of study treatment. All SAEs will be followed up until resolution or stabilisation.

Injection site reactions will be assessed by type and grade and recorded in the patient's eCRF before each injection of IMM-101. These will only be recorded as an AE if deemed appropriate by the Investigator, but any injection site reactions of Grade  $\geq$ 3 (Section 9.2.4) should be recorded as an AE.

#### 9.6 APPROPRIATENESS OF MEASUREMENTS

All laboratory and other safety assessments (vital signs, weight, physical examination, pregnancy tests, etc.) are regarded as standard, i.e., are widely used and generally recognised as reliable, accurate and relevant.

For all patients in the study, the maximum volume of blood collected per patient at a single visit specifically for the safety endpoints will not exceed 10mL. For patients in cohort A, an additional 25mL of whole blood will be taken for immunological marker analysis at Screening,

Page 70 of 98

Week 4, Week 8, Week 12, Week 20, and every 8 weeks thereafter until Week 52 or EOS, if this is sooner. For patients in cohort B, an additional 25mL of whole blood will be taken for immunological marker analysis at Screening, Week 6, Week 14, Week 22, and every 8 weeks thereafter until Week 46 or EOS, if this is sooner.

Due to the need to evaluate the biomarker, PD-L1, that may be predictive of treatment benefit, biopsy samples are collected at Screening from all patients in cohort A of the study. Subsequent tumour biopsies from patients in cohort A at Week 12 will be valuable in exploratory research into biomarkers that may help to further elucidate the activity of the IMM-101 + nivolumab combination. However, the collection of samples is subject to the patient providing consent. For patients in cohort B, a biopsy sample at Screening will be taken subject to the patient's consent and also providing that scheduling the procedure will not cause any delay to the patient's treatment for those who are on-going with anti-PD1 therapy. Patients in cohort B who have provided a biopsy sample at screening will also be asked for consent for a further biopsy sample taken from the same lesion as at Screening if they should show a response to study treatment.

# 9.7 RECORDING AND REPORTING ADVERSE EVENTS AND INTERCURRENT ILLNESSES

It is the responsibility of the Investigator to document all AEs that occur during the study from patient entry (i.e., informed consent). An AE includes any noxious, pathological or unintended change in anatomical, physiological or metabolic functions as indicated by physical signs, symptoms and/or laboratory changes whether or not associated with the study drug and whether or not considered related to the study drug. This includes an exacerbation of pre-existing conditions or events, intercurrent illnesses or drug interaction. Anticipated day-to-day fluctuations of pre-existing conditions that do not represent a clinically significant exacerbation or worsening need not be considered AEs.

Patient entry into the study is defined as the time at which informed consent is obtained (this must be before any protocol-specific diagnostic procedures or interventions). All AEs that occur after informed consent has been provided must be reported regardless of whether or not they are considered drug related.

Adverse events will be elicited by asking the patient a non-leading question, for example "Have you experienced or are you experiencing any new or changed symptoms since we last asked/since your last visit?" All AEs must be reported on the appropriate page of the patient's eCRF.

All AEs occurring in patients receiving nivolumab or ipilimumab should be reported irrespective of whether they are identified as being expected as per the product labelling or not.

Each AE will be assigned a CTCAE severity/intensity category as described in Section 9.2.4.

If there is a change in severity of an AE, it must be recorded in the patient's eCRF.

Every effort should be made by the Investigator to explain each AE and assess its relationship, if any, to study drug treatment (IMM-101, nivolumab and, if used on study for patients in cohort B, ipilimumab). Causality should be assessed using the categories as described in Section 9.2.3.

The Investigator must report in detail all adverse signs and symptoms following obtaining informed consent which are either volunteered by patients or observed during or following the course of investigational product administration.

Page 71 of 98

In the event of a SAE/SUSAR, the Investigator will also complete the SAE Report form and forward to Bionical-Emas, by email or fax, within 24 hours:

SAE CONTACT DETAILS: Bionical-Emas Ltd.

# 9.7.1 Pregnancy Reporting

Pregnancy is not considered an SAE. If a female participant, or the female partner of a male participant, becomes pregnant after exposure to study product, the pregnancy must be reported to Bionical-Emas within 24 hours of the Site Staff becoming aware of the Pregnancy. A Pregnancy Reporting Form must be completed and emailed or faxed to Bionical-Emas.

In the event of a pregnancy being reported after exposure to study product, the pregnant woman should be followed to completion/termination of the pregnancy and the outcome of the mother and infant should be reported in follow-up using the Pregnancy Reporting Form.

If a congenital anomaly or birth defect occurs, this must be reported to Bionical-Emas by the submission of a completed SAE form.

#### 9.8 ADVERSE EVENT FOLLOW-UP PROCEDURES

All SAEs will be followed to resolution. All non-serious AEs will be followed until the event has resolved (disappeared) or until they have stabilised, and the relationship to the study drug is clarified. AEs will be followed until resolution, death or 30 days after the last administration of study treatment (whichever comes first). The Investigator may contact the patient by telephone to obtain the information.

#### 10. EFFICACY ASSESSMENTS

#### 10.1 OVERALL RESPONSE RATE

In this study, Overall Response Rate (ORR) is calculated from assessments of Best Overall Response (BOR) per RECIST 1.1. ORR is defined as the number of patients with a BOR of CR or PR divided by the number of ITT patients in each cohort of the study. For cohort B, ORR will be evaluated from assessments of BOR up until the point of change of treatment on study to IMM-101 + ipilimumab, where applicable. An interim data review on each respective cohort will be conducted after all cohort B patients have had the opportunity for 6 months on study, and when all cohort A patients have had the opportunity for 12 months on study.

ORR calculated from BOR according to Immune-Related Response (irRC) will be used as a secondary efficacy parameter and will be calculated similarly.

# **10.1.1** Overall Response

# 10.1.1.1 Overall Response by RECIST 1.1

For RECIST 1.1, Overall Response at any time point is evaluated based on target lesion response, non-target lesion response and any new lesions identified on a post-baseline scan. An Overall Response of CR, PR, SD, or PD at each scan assessment is made according to the guidelines in **Table 2**:

Table 2: Time Point Overall Response - RECIST 1.1				
Target Lesions	Non-target Lesions	New Lesions	Overall Response	
CR	CR	No	CR	
CR	Non-CR/non-PD	No	PR	
CR	Not evaluated	No	PR	
PR	Non-PD or not all evaluated	No	PR	
SD	Non-PD or not all evaluated	No	SD	
PD	Any	Yes or No	PD	
Any	PD	Yes or No	PD	
Any	Any	Yes	PD	
Not all evaluated	Non-PD	No	NE	

CR = complete response, PR = partial response, SD = stable disease, PD = progressive disease, and NE = inevaluable

# 10.1.1.2 Overall Response by irRC

For irRC, overall response at any time point is evaluated on the change in tumour burden which is calculated from index (target) and new, measurable lesions only:

Tumour Burden =  $SPD_{index lesions} + SPD_{new, measurable lesions}$ 

Page 73 of 98

Non-measurable lesions do not contribute to the tumour burden. However, new non-measurable lesions (ie  $\leq$  5 x 5 mm) do preclude assigning CR.

Overall Response is evaluated according to the following rules:

Complete Response (irCR): Disappearance of all target lesions; no new lesions that are either measurable or non-measurable.

Partial Response (irPR): At least a 50% decrease in tumour burden, calculated as above, taking as reference the baseline SPD calculation.

Progressive Disease (irPD): At least a 25% increase in tumour burden taking as reference the lowest tumour burden on study (this includes the baseline SPD if that is the smallest on study).

Stable Disease (irSD): Neither sufficient shrinkage in tumour burden to qualify for PR (compared to baseline) nor sufficient increase to qualify for PD (compared to the smallest tumour burden while on study).

# **10.1.2 Best Overall Response**

Best Overall Response (CR, PR, SD or PD) is determined as the best response designation, recorded from the first post-screening scan until and including the last imaging assessment on study for each patient. All scans will be evaluated for overall response and BOR will be calculated based on overall response designations determined by the Investigator, from all scan assessments. However, for any patients in cohort B who change treatment on study to IMM-101 + ipilimumab, BOR will be assessed both before a change to ipilimumab for patients to whom this applies (for evaluation of ORR), and also from all tumour assessments on study.

BOR according to both RECIST 1.1 criteria and irRC criteria will be determined.

For cohort A, BOR will be assessed at the time point when all patients have had the opportunity for 12 months on study (RECIST 1.1 only), and again at the end of the study. For the first assessment, the BOR will be the best response designation, as determined by the Investigator, recorded from the first post-screening scan until the last scan prior to or at the 12 month time point for each patient on study.

For cohort B, BOR will be assessed at the time point when all patients have had the opportunity for 6 months on study (RECIST 1.1 only) and again at the end of study or when all patients in this cohort have withdrawn if this is sooner. For the first assessment, the BOR will be the best response designation, as determined by the Investigator, recorded from the first post-screening scan until the last scan prior to or at the 6 month time point for each patient on study. For any patients in cohort B of the study who change treatment on study to IMM-101 + ipilimumab, BOR will be assessed both before a change to ipilimumab for patients to whom this applies (for evaluation of ORR), and also from all tumour assessments on study.

In this study, the minimum scan time from Screening for determination of SD will be 9 weeks.

Confirmed response is used for calculation of BOR (Section 8.5.3.10); however unconfirmed results will also be analysed and corresponding BOR and ORR reported for comparability with published data.

Page 74 of 98

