## 5.3 ASSESSMENT OF RESPONSE

Baseline assessments should be performed within 21 days prior to the first dose and all known and suspected sites of disease should be assessed. The preferred method is contrast enhanced CT of the chest, abdomen and pelvis. A baseline MRI of the brain should be done for patients with a history or clinical symptoms of brain metastases. MRI can be used as an alternative method to CT scan if the patient has a clinical contraindication for iodine-based IV contrast or to better assess the disease. CT head scan can be used as an alternative to MRI of the brain if IV gadolinium is contraindicated.

All scans will be reviewed by an experienced radiologist trained in the study requirements. The scans will be read in sequence, and each review should be within 4 weeks of the scan being conducted to ensure that a confirmatory scan can be conducted as required.

Baseline scans will be assessed (and non-target/target lesions identified from the baseline scan alone) prior to the review of post baseline scans.

Where possible, the same radiologist should review the scan for both RECIST and irRC at the same time, and review all scans for the same patient.

Further details are provided in the IMM-101-015 Study Operations Manual.

Subsequent assessments should use the same imaging method as was used at baseline. At least one measurable lesion is required to be present at baseline based on the RECIST (version 1.1) definition of a measurable lesion.

Standard RECIST is used in this study for the main assessment of response to ensure comparability with published data. Immune Related Response Criteria (irRC) is also used in this study for assessment of response and may be used for the purposes of managing patients on protocol treatment and decision making for discontinuation of study therapy due to disease progression.

Assessment of response is based on scans at baseline, with the first scheduled scan at week 12 ( $\pm 7$  days) (cohort A) and week 6 ( $\pm 7$  days) (cohort B) and then at 8 weekly intervals ( $\pm 7$  days) thereafter on study. Beyond week 52, scans may be conducted every 12 weeks ( $\pm 7$  days) at the discretion of the investigator.

For each post-baseline scan, patients will be assigned one of the following categories:

- Complete response
- Partial response
- Stable disease
- Progression

Page 35 of 98

• Inevaluable for response (specify reasons)

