Ultrasound should not be used for lesion measurement. If new lesions are identified by ultrasound in the course of the study, confirmation by CT or MRI should take place.

Endoscopy and laparoscopy should not be used for objective tumour evaluation.

Immune Related Response Criteria (irRC) is also used in this study for assessment of response and may be used for the purposes of managing patients on protocol treatment and decision making for discontinuation of study therapy due to disease progression. For the purposes of irRC, up to five lesions in a single organ may be recorded with a maximum of 10 visceral and five cutaneous index lesions (see Section 8.5.2.3). The first post-baseline radiological assessment of tumour response status will be performed at Week 12 (±7 days) for patients in cohort A and at Week 6 (±7 days) for patients in cohort B unless there is clinical indication (based on Investigator's assessment) warranting earlier imaging. Subsequent radiological assessments are at 8 weekly intervals thereafter on study. Beyond week 52, scans may be conducted every 12 weeks at the discretion of the investigator.

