#### 10.6 DISEASE CONTROL

Disease Control will be assessed for patients in cohort B of the study only and is defined as those patients with a response (CR or PR) or SD based on RECIST 1.1. The minimum scan time from Day 0 (date of first IMM-101 dose) for determination of Stable Disease (SD) is 9 weeks. Stable disease for patients in Cohort B can therefore be first assessed at the second scan on study (Week 14) since the first scheduled scan is at 6 weeks. If unscheduled scans take place earlier than Week 14 but later than Week 9, these may be used for determination of SD. The disease control rate is evaluated for treatment with IMM-101 + nivolumab only and is the number of patients with disease control at each scheduled scan time point divided by the number of patients in cohort B. For patients who change treatment to IMM-101 + ipilimumab, disease control is assessed until and including the last evaluable tumour assessment (scan) prior to the change in therapy, and the disease control rate evaluated accordingly.

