#### 11.2 SAMPLE SIZE

Sufficient patients will be screened for 18 patients to be enrolled into cohort A and 8 into cohort B of this open-label study. Patients withdrawn after first treatment with IMM-101 will not be replaced. No formal sample size calculation has been performed and the sample size is considered a sufficient and adequate number of patients to investigate the efficacy signals of IMM-101 combined with nivolumab in controlling advanced melanoma and to explore the safety profile of the combination therapy.

Page 80 of 98

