5.13 EFFICACY EVALUATION

5.13.1 Primary Endpoint

The primary endpoint will be analysed using the ITT set and repeated for the PPS for Cohort A only.

Primary Analysis

The primary efficacy endpoint of the study is the ORR calculated from the BOR of subjects as assessed by RECIST 1.1.

The investigator response will be entered into the Response Assessment (RECIST 1.1) page of the electronic Case Report Form (eCRF) at each scan assessment to be used in the derivation of BOR.

A confirmed response will be used in the derivation of BOR. A confirmed response is defined as a response obtained from a scan repeated at least 4 weeks following a scan with designation of complete response (CR) or partial response (PR), as defined using Table 3 of RECIST 1.1. In addition, the following approaches will be taken:

- Where a confirmatory assessment is non-evaluable (NE) but the subsequent scan maintains the same response/progression, the response/progression will be considered confirmed (e.g. PR-NE-PR).
- Subjects without a confirmed response of CR or PR will have their next best response (stable disease (SD) or otherwise progressive disease (PD)) assigned as their BOR.
- Subjects without a BOR assessment, such as those with no post-baseline responses or only NE responses, will be assumed to have a BOR of PD using a worst-case approach.

For Cohort A, BOR is defined as the best confirmed response designation, recorded from the first post-baseline scan until and including the last scan on study for each subject.

For Cohort B, BOR is defined as the best confirmed response designation, recorded from the first post-baseline scan until and including the last scan on study for each subject for those receiving IMM-101 and nivolumab, or the last scan performed prior to treatment with ipilimumab. No scan performed once ipilimumab treatment commences will be included.

All scans within these periods, whether scheduled or unscheduled, will be evaluated for overall response.

ORR is calculated as the number of subjects with a BOR of confirmed CR or PR divided by the number of subjects in the analysis set. ORR is calculated for each cohort separately.

Summaries of BOR (best confirmed overall response designation)

The BOR will be summarised for each cohort. The ORR and accompanying exact binomial 95% confidence intervals (CI) will also be presented.

Listings of lesions assessments and BOR

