5.13.3.3 Time to Response Assessed by RECIST 1.1 for Cohorts A and B

Time to response will be analysed using the ITT set and only subjects who have a documented response of CR or PR will be included.

Time to response is calculated as the time in months from Visit 1 to the first documented response of CR or PR per RECIST 1.1 (date of documented response – date of Visit 1 + 1). All scans are considered, whether scheduled or unscheduled, in the determination of response and confirmed responses are not required.

For Cohort B subjects who change treatment to IMM-101 and ipilimumab, only responses evaluated until the point of this change in therapy are included.

Summaries of time to response

Descriptive statistics will be presented for time to response. KM estimates for the 25th, 50th and 75th percentiles for the time to response and corresponding 95% CIs will be presented. The proportion of subjects who have not achieved complete or partial response at 3 monthly intervals will also be presented.

5.13.3.4 Disease Control Assessed by RECIST 1.1 for Cohort B from Week 14 Onwards

Disease control will be analysed using the ITT set for Cohort B only.

Disease control is defined as a subject with a response of CR, PR or SD as per RECIST 1.1. Confirmed responses are not required.

SD determination requires a minimum scan time of 9 weeks from the first administration of IMM-101. Therefore, the first scan to be considered for this determination is Week 14. If unscheduled scans take place earlier than Week 14 but later than Week 9, they will be used for determination of SD for disease control at Week 14. For further information on the scan windows see Section 5.2.4 of this SAP.

Disease control is assessed at each scheduled scan assessment from Week 14 until the end of the study. For subjects who change treatment to IMM-101 and ipilimumab, only responses evaluated until the point of this change in therapy are included.

Disease control rate is calculated as the number of subjects with disease control divided by the number of subjects in the analysis set.

Summaries of Disease Control

The number of subjects with controlled disease and the number without controlled disease will be summarised together with the disease control rate for each scheduled scan assessment. The binomial 95% CIs will also be presented.

Disease control will be listed for each subject in Cohort B for each Visit.

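### The 9-week minimum for stable disease starts at Screening for BOR but at first dose for disease control, and the SAP's BOR rule has no minimum, so a Cohort B Week 6 SD can be classed in different ways

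*Protocol*

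**What the plan says.** Three places bear on when an SD reading counts.

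- **Protocol 10.1.2 (BOR):** "the minimum scan time from Screening for determination of SD will be 9 weeks". Screening is not tied to a date here.
- **Protocol 10.6 (disease control, Cohort B only):** "The minimum scan time from Day 0 (date of first IMM-101 dose) for determination of Stable Disease (SD) is 9 weeks". It adds that SD in Cohort B "can therefore be first assessed at the second scan on study (Week 14) since the first scheduled scan is at 6 weeks", and it accepts unscheduled scans between Week 9 and Week 14. SAP 5.13.3.4 repeats this start point for disease control: "SD determination requires a minimum scan time of 9 weeks from the first administration of IMM-101".
- **SAP 5.13.1 (derivation of BOR):** subjects lacking a confirmed CR or PR "will have their next best response (stable disease (SD) or otherwise progressive disease (PD)) assigned as their BOR". All scans in the evaluation period are used, scheduled or not. No minimum time for SD and no start point are given. Subjects with no BOR assessment, such as those with no post-baseline response or only non-evaluable ones, are set to PD as a worst case.

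SAP section 6, which lists departures from the protocol's planned analysis, does not mention the SD minimum.

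**The concern.** The protocol sets one limit with two start points, and the SAP section that produces the BOR table carries neither. A programmer could defend three rules for BOR: 9 weeks from Screening, 9 weeks from first dose, or no minimum.

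The case that separates them is built into the design. Cohort B has its first scan at Week 6 and its second at Week 14. Patients may switch to ipilimumab on RECIST or clinical progression, and scans after ipilimumab starts do not enter the primary BOR. A patient can therefore have SD at Week 6 as the only non-progressive reading in the BOR period. Whether that patient appears as SD then depends on which rule is programmed. The trial is open-label, so a choice left until the tables are run would be made with outcomes visible.

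**Working it through.** **Inputs**

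- Minimum for SD: 9 × 7 = 63 days (Protocol 10.1.2 and 10.6).
- Study day of the first Cohort B scan, *s*: the scan is "at Week 6 (±7 days) for patients in cohort B" (Protocol 8.5.1), so *s* = 42 ± 7 = 35 to 49, which is 15 possible days.
- Days from baseline scan to Day 0, *b*: "Baseline assessments should be performed within 21 days prior to the first dose" (Protocol 5.3). I take *b* = 1 to 21, because Screening runs from Day -21 to Day -1 (Protocol 8.1).
- Cohort sizes: "18 patients to be enrolled into cohort A and 8 into cohort B" (Protocol 11.2). The interim review of ORR uses 5 Cohort B subjects (SAP 4.2).

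**Step 1. Reproduce the protocol's own figure (start at Day 0).** The interval is *s*. For Week 6 it is 35 to 49 days, so 0 of 15 scan days reach 63. For Week 14 it is 98 ± 7 = 91 to 105 days, so all qualify. Week 14 is the first scheduled scan that can give SD, as Protocol 10.6 says.

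**Step 2. Start at Screening, read as the baseline scan.** The interval is *b* + *s*, from 1 + 35 = 36 to 21 + 49 = 70 days. It qualifies when *s* ≥ 63 − *b*.

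| Baseline scan before Day 0 (*b*) | Week 6 scan days that qualify |
|---|---|
| 13 days or fewer | none (needs day 50 or later) |
| 14 days | 49 |
| 18 days | 45 to 49 |
| 21 days | 42 to 49 |

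An on-time day-42 scan qualifies only with *b* = 21. The qualifying date pairs number 1 + 2 + … + 8 = 36 (for *b* = 14 to 21), out of 21 × 15 = 315 allowed pairs. This is a count of combinations, not a probability.

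**Step 3. SAP 5.13.1 read literally.** There is no minimum, so an SD on any of the 15 scan days counts.

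**Step 4. Which patients are affected.** Later scheduled scans pass under every rule: Week 14 in Cohort B (91 to 105 days from Day 0) and Week 12 in Cohort A (84 ± 7 = 77 to 91 days). On scheduled scans, the rules can disagree only for a Cohort B patient with SD at Week 6 and no later qualifying SD or response in the BOR period.

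| Start point | Is BOR SD for that patient? |
|---|---|
| Day 0 | never |
| Screening (baseline scan) | only if *b* is 14 to 21 and *s* ≥ 63 − *b* |
| None (SAP 5.13.1, literal) | always |

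**Step 5. Size.** One patient is 1/8 = 12.5 points of the planned Cohort B table and 1/5 = 20 points at the interim. The ORR numerator is confirmed CR plus PR and the denominator is the ITT set. Neither uses SD, so ORR and its exact interval do not move.

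**The case against.** The strongest reply is that nothing inferential depends on this. All endpoints are descriptive, ORR is untouched, and disease control has an explicit first-dose start point in both documents. The two protocol start points also disagree only in a narrow set of dates. All of that stands, and it limits the point to the SD row of the Cohort B BOR table and whichever row an early SD would otherwise enter.

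A second reply is that the intent is clear from Protocol 10.6, or that Screening in 10.1.2 means the end of Screening. Counted from Day -1, the Week 6 interval would be 36 to 50 days and would never reach 63, in agreement with Day 0. This is possible, but 10.1.2 does not say so. Counting from the start of Screening, up to 21 days before Day 0, gives the same kind of date dependence as Step 2. Neither reading supplies the minimum missing from SAP 5.13.1. That section cites Table 3 of RECIST 1.1 when defining a confirmed response. The table is not reproduced, so what it adds for SD cannot be settled from these documents, and the SAP says the unconfirmed-response analyses need not follow it.

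A reader might also infer two further harms. One is that patients with identical disease are classed differently by scan date alone. Any minimum-interval rule does that, including one from Day 0, because unscheduled scans after Week 9 are accepted. The other is that a patient could be SD in BOR yet not controlled. That happens by design, since disease control is judged scan by scan and BOR over the whole period: SD at Week 14 followed by PD at Week 22 gives both. Neither harm is evidence of this inconsistency.

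**Conclusion.** The point holds, and it is minor. The current protocol text gives two start points for one limit, and the SAP's BOR rule drops the limit. Read literally, the SAP accepts every Cohort B Week 6 SD, although Protocol 10.1.2 sets a 9-week minimum for BOR. The larger gap is between the SAP (always SD) and a Day 0 rule (never SD). The Screening rule lies between them.

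The size is 12.5 points of the Cohort B BOR table per affected patient, or 20 points at the interim. The documents do not allow a forecast of how many patients will be affected. It would be wrong to conclude that the primary efficacy result is at risk, because SD enters neither ORR nor its interval.

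The Screening figures assume that Screening means the baseline scan, done 1 to 21 days before first dose, with the Week 6 scan inside its window. The Day 0 and literal-SAP results do not depend on the baseline scan date.

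**What to change.** In SAP 5.13.1, state that SD counts toward BOR only from a scan at least 9 weeks after the first IMM-101 dose, matching Protocol 10.6 and SAP 5.13.3.4. List the change in SAP section 6 and align Protocol 10.1.2.

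The start point alone is not enough, because no section says what becomes of an SD seen too early. The SAP's worst-case rule is written for subjects without a BOR assessment and does not clearly cover them. Add that a subject whose only SD falls before 9 weeks is classed PD if PD follows, and otherwise comes under that existing worst-case rule.

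The cost is a few sentences in the SAP and one aligned sentence in the protocol. Protocol 11.6 allows departures from the planned analysis to be documented in the final SAP, so the analysis rule need not wait for a protocol amendment. The downside is that the Cohort B SD rate may be slightly lower. The edit should be made before any BOR table is produced.
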